To assess the response rate of subjects to galcanezumab in vestibular migraine, as measured by a 100%, 75%, 50%, and 25% reduction in definitive dizzy days, comparing baseline data (month 0 to 1), to after treatment data (months 3-4), comparing between active treatment and placebo arms.

To assess the time course of response to galcanezumab in vestibular migraine, measured by definitive dizzy days per month, comparing active treatment and placebo arms, from months 0 to 4.

To assess the efficacy of galcanezumab in treating vestibular migraine, as assessed by DHI (Dizziness Handicap Inventory) score change between baseline (month 0) and after three months of treatment (month 4), comparing active treatment and placebo arms.

To assess the efficacy of galcanezumab in treating quality of life in vestibular migraine, comparing the change in baseline PROMIS SF v1.2- Global Health scores to scores after 3 months of treatment (at month 4), across active treatment and placebo arms.

Study Endpoints:

Primary:

VM-PATHI (Vestibular Migraine Patient Assessment Tool and Handicap Inventory) score.

Secondary:

Definitive dizzy days, measured with a daily text message, with any day where dizziness is rated as a 2 (moderate) or higher counting as a definitive dizzy day.

Response rates, as measured by percentage of subjects in each arm experiencing a 100%, 75%, 50%, 25%, 0% reduction in definitive dizzy days.

Dizziness Handicap Inventory
PROMIS SF v1.2- Global Health

Statistical Methods:

Primary Endpoint:

VM-PATHI score changes between baseline and after treatment (month 4) will be compared between active treatment and placebo arms using a paired two-tailed t-test.

Secondary Endpoint:

Definitive dizzy days/month, comparing baseline to after treatment, between active treatment and control arms, will be assessed using a paired two-tailed t-test.

Response rates will be reported per category (100%, 75%, 50%, 25%, and 0%) for both active treatment and control arms. Number of subjects who experience 50% or better reduction in dizziness days will be compared using chi squared test.

Dizziness Handicap Inventory will be compared between active treatment and control arms, looking at change in score from baseline to month 4, using a paired two-tailed t-test.

PROMIS scores, comparing subdomain score changes from before (month 0) and after (month 4) treatment, across active and placebo arms, using paired t-test

Subject Selection:

Inclusion criteria:

- Adult age 18 to 75

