This will be a single center, randomized double-blinded placebo-controlled trial comparing galcanezumab to placebo for treatment of vestibular migraine. Screening data will be reviewed to determine subject eligibility. Subjects who meet all inclusion criteria and none of the exclusion criteria will be entered into the study. Patients in the galcanezumab arm will receive 240 mg via subcutaneous injection with a pre-loaded syringe at month 1, followed by 120 mg at month 2, and 120 mg at month 3. Those in the placebo arms will receive subcutaneous injections at the same time intervals of placebo. This will be a single institution study, and randomization will occur through the hospital research pharmacy. Allocation concealment will be ensured; study participants will be given an envelope from a folder of sequentially ordered identical envelopes that will contain study instructions and the allocated drug. The master file linking study ID with allocation will be created by a third party and kept secret until after data analysis is complete. This will ensure that both providers and participants are adequately blinded. Blocking will be used in increments of 10 subjects to ensure equitable distribution of subjects into the two treatment arms. In addition, stratification by sex and definite versus probable vestibular migraine status will be used to ensure equal allocation. Total duration of subject participation will be five months. Total duration of the study is expected to be 2 years.

Inclusion Criteria

1. Male or female aged 18 to 75 years of age at Study Visit 1.
2. Documentation of a vestibular migraine or probable vestibular migraine diagnosis according to the following criteria determined by the Barany Society:

- Vestibular migraine
 - A: At least 5 episodes with vestibular symptoms of moderate or severe intensity, lasting 5 min to 72 hours
 - B: Current or previous history of migraine with or without aura according to the International Classification of Headache Disorders (ICHD)
 - C: One or more migraine features with at least 50% of the vestibular episodes:
 - headache with at least two of the following characteristics: one sided location, pulsating quality, moderate or severe pain intensity, aggravation by routine physical activity
 - photophobia and phonophobia
 - visual aura
 - D: Not better accounted for by another vestibular or ICHD diagnosis
- Probable vestibular migraine

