 - At least 5 episodes with vestibular symptoms of moderate or severe intensity, lasting 5 min to 72 hours
 - Only one of the criteria B and C for vestibular migraine is fulfilled (migraine history or migraine features during the episode)
 - Not better accounted for by another vestibular or ICHD diagnosis

3. Written informed consent obtained from subject and ability for subject to comply with the requirements of the study.
4. Baseline (SV1) and SV2 VM-PATHI score > 25
5. Baseline (month 0 to 1) definitive dizzy days > 4
6. Fluency in English
7. 80% adherence or better to daily text message during baseline phase
8. Written informed consent
9. Access to email, and cell phone

a. Exclusion Criteria

1. Pregnant, breastfeeding, or unwilling to use approved form of birth control during participation in the study.
2. Presence of a condition or abnormality that in the opinion of the Investigator would compromise the safety of the patient or the quality of the data.
3. Allergy to galcanezumab
4. Prior treatment with galcanezumab
5. History of ear surgery (other than ear tubes)
6. Other vestibular diagnosis (excluding treated BPPV- Benign Paroxysmal Positional Vertigo). This includes Meniere's disease, superior canal dehiscence syndrome, vestibular neuritis,

persistent postural perceptual dizziness, unilateral or bilateral vestibular loss, cerebellar or brainstem disease, multiple sclerosis, Mal de Debarquement, Third window syndrome, vestibular paroxysmia, vestibular schwannoma, psychiatric dizziness, central dizziness, multifactorial dizziness, dizziness due to cerebrovascular disease, post-concussive dizziness, and cervicogenic dizziness.

7. Failure of treatment with > 4 prophylactic migraine medications
8. Prior or current treatment with a CGRP medication
9. Pregnant/breastfeeding if female
10. History of serious medical or psychiatric disease, at the discretion of the treating physician (including significant coronary artery disease, peripheral vascular disease, cerebrovascular disease, kidney disease, liver disease, Raynaud's disease, uncontrolled psychiatric disease or past psychiatric hospitalization)
11. History of mania, psychosis, or suicidal ideations
12. Ok if on up to 2 migraine prophylactic medications (prescribed for that purpose), dose must be stable for 2 months prior to study start.

Rationale:

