- Early Discontinuation of Study Drug:**

- o A subject may be discontinued from study treatment at any time if the subject, the investigator, or the Sponsor feels that it is not in the subject’s best interest

to continue. The following is a list of possible reasons for study treatment discontinuation:

- Subject withdrawal of consent (or assent)
- Subject is not compliant with study procedures
- Adverse event that in the opinion of the investigator would be in the best interest of the subject to discontinue study treatment
- Protocol violation requiring discontinuation of study treatment
- Lost to follow-up
- Sponsor request for early termination of study
- Positive pregnancy test (females)

If a subject is withdrawn from treatment due to an adverse event, the subject will be followed and treated by the Investigator until the abnormal parameter or symptom has resolved or stabilized. All subjects who discontinue study treatment should come in for an early discontinuation visit as soon as possible and then should be encouraged to complete all remaining scheduled visits and procedures. All subjects are free to withdraw from participation at any time, for any reason, specified or unspecified, and without prejudice. Reasonable attempts will be made by the investigator to provide a reason for subject withdrawals. The reason for the subject's withdrawal from the study will be specified in the subject's source documents.

c. Analysis of Primary Endpoint:

d. For the primary endpoint, which is the change in VM-PATHI scores between month 1 and month 4 as compared between the galcanezumab arm and the placebo arm, a paired two-tailed Student's t-test will be used, provided the data is normally distributed. This will be conducted with an intent-to-treat analysis. Significance will be set at alpha of 0.05.

e. Analysis of Secondary Endpoints:

Definitive dizzy days/month, comparing baseline (month 0 to 1) to after treatment (month 3-4), between active treatment and control arms, will be assessed using a two-tailed t-test.

Response rates will be reported per category (100%, 75%, 50%, 25%, and 0% reduction in definitive dizziness days, comparing month 0 to 1 to month 3 to 4) for both active treatment and control arms. Number of subjects who experience 50% of better reduction in dizziness days will be compared using Chi Squared test.

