Dizziness Handicap Inventory will be compared between active treatment and control arms, looking at change in score from baseline to month 4, using a two-tailed t test.

PROMIS scores comparing active and placebo arm score changes from before (month 0) and after (month 4) treatment using a paired t-test.

Safety and tolerability data will be summarized by treatment group.

Adverse event rates will be coded by body system and MedDra classification term. Adverse events will be tabulated by treatment group and will include the number of patients for whom the event occurred, the rate of occurrence, and the severity and relationship to study drug.

Initially data will be summarized overall, by patient, and by treatment and control groups. Plots of each outcomes will be displayed graphically over longitudinal time points. Univariate summaries of all variables overall, by patient, and by subgroup will include means and standard deviations for continuous variables and counts and percentages for categorical variables.

Bias:

Bias will be minimized by using a double-blinded study design, with allocation concealment. This will limit selection, performance, and detection bias. In addition, this will help control for potential confounding variables. In addition, by including a placebo control group, we will minimize regression to the mean bias. Finally, by collecting information prospectively, we will minimize reporting bias.

Missing Data:

We will minimize missing data by having the clinical trial coordinator present to help the study subject fill out all data. We anticipate a 15-20% loss to follow up, and have accounted for that in our sample size calculations. Outliers and non-compliant subjects will be included in the analysis. We will perform an intent-to-treat analysis.

Trial Duration:

We estimate that this trial will take approximately 2 years to complete, once subject recruitment is able to begin. That includes 1.5 years for subject recruitment and data collection, and 6 months for closeout and data analysis. If recruitment is slower than expected, we will plan on keeping the trial open for a longer period of time. This seems unlikely based on our prior experience with recruitment in this patient population.

Pharmacy/Study Drug:

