Appendix 1: Schedule of study events

Study month	0	1	2	3	4
Clinical Visit	✓ (L5) SV 1	✓ (L4) SV 2	✓ (L4) SV 3		✓ (L4) SV 4
Phase of study	Baseline Eval	Randomize/Start Treatment	First eval on Tx		Final eval for data/safety
Testing	CBC	✓			✓
	CMP	✓			✓
	EKG	✓			✓
	Pregnancy Test	✓			
	Audio (if not previously done)	✓			
	Vital signs	✓	✓	✓	✓
Questionnaires	VM-PATHI	✓	✓	✓	✓
	DHI		✓	✓	✓
	HIT-6		✓	✓	✓
	PROMIS SF v1.2- Global Health		✓		✓
	Med review	✓	✓	✓	✓
	Adverse Effects			✓	✓
	Medical history	✓			
	Demographics	✓			
	PHQ-9		✓		✓
	GAD-7		✓		✓

	Diagnosis form	√				
	Close-out form					√
Definitive Dizzy Day Text		√	√	√	√	√
Treatment			240 mg Emgality/Placebo	120 mg	12 0 mg	

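### Definitive dizzy days, DHI and PROMIS are compared by t-test with no covariates; adjusting for the pre-treatment value and the randomisation strata would usually add precision at almost no cost

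*Combined protocol and SAP*

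**What the plan says.** The section Analysis of Secondary Endpoints specifies a two-tailed t-test for dizzy days, in a sentence that opens "Definitive dizzy days/month, comparing baseline (month 0 to 1) to after treatment (month 3-4), between active treatment and control arms, will be assessed using a". For DHI the arms are compared "looking at change in score from baseline to month 4, using a two-tailed t test". For PROMIS the text is "PROMIS scores comparing active and placebo arm score changes from before (month 0) and after (month 4) treatment using a paired t-test".

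The earlier Statistical Methods summary lists the same comparisons but calls all three tests paired, for example "Definitive dizzy days/month, comparing baseline to after treatment, between active treatment and control arms, will be assessed using a paired two-tailed t-test". No section names a covariate, a stratum term or a regression model for these endpoints.

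The candidate covariates are already collected:

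- **Dizzy days.** The count is an entry criterion, "Baseline (month 0 to 1) definitive dizzy days > 4", with at least 80% text adherence, and the Randomization section makes allocation depend on final eligibility at SV2. Everyone randomised therefore has a baseline count.
- **DHI and PROMIS.** "Appendix 1: Schedule of study events" appears to place the first DHI and PROMIS at month 1 (SV2), although the table layout is partly broken. The DHI objective and the PROMIS analysis text put baseline at month 0.
- **Strata.** Study Design states that "stratification by sex and definite versus probable vestibular migraine status will be used to ensure equal allocation".

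**The concern.** A change score subtracts the whole baseline, which fixes the baseline slope at 1. When the true slope is below 1, this over-corrects: an arm that happens to start higher will appear to improve more. Dizzy days are not a stratification factor, so nothing in the design balances them between two arms of about 25.

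The background section gives the pilot's purpose as gathering treatment effect sizes for a larger study. A noisier estimate that depends on the luck of the baseline draw passes into that planning. The point concerns the secondary endpoints only, not the VM-PATHI primary.

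**Working it through.** **Inputs from the documents.** 25 per arm, 1:1 allocation, alpha 0.05 (stated for the primary), and 15-20% expected loss to follow-up in the Missing Data section, hence 20 per arm as the low case. The only stated power, 90% for a 7-point difference, concerns VM-PATHI. It cannot be reproduced because its SD has no number, and it does not bear on these endpoints.

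**Assumed.** No effect, SD or correlation is given for dizzy days, DHI or PROMIS. Rho is varied from 0.3 to 0.9, and 80% power for the change test is used only as a reference point.

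**Step 1: variance.** Let the baseline SD be 1 and the follow-up SD be k. Per subject:

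- change score: 1 + k² − 2·rho·k
- baseline-adjusted: k²(1 − rho²)

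The difference is (1 − rho·k)², which is never negative. Before covariate cost, adjustment therefore cannot lose. With k = 1 the ratio of adjusted to change variance is (1 + rho)/2: 0.65, 0.75, 0.85 and 0.90 at rho 0.3, 0.5, 0.7 and 0.8, that is, cuts of 35, 25, 15 and 10%.

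**Step 2: cost of three covariates.** If sex and diagnosis predict nothing, multiply by 1 + 3/(2n − 6), which is 1.068 at n = 25 and 1.088 at n = 20. At n = 25 and rho 0.5 this gives 0.75 × 1.068 = 0.80.

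**Step 3: power.** For the change test with 48 df, 80% power needs a noncentrality of 2.859. Divide by the square root of the step 2 ratio and read power from the noncentral t with 2n − 5 df. At rho 0.5: 2.859/√0.801 = 3.194, giving 87.8%. At n = 20 the starting noncentrality is 2.875.

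| rho | ratio, n = 25 | power, n = 25 | ratio, n = 20 | power, n = 20 |
|---|---|---|---|---|
| 0.3 | 0.69 | 91.9% | 0.71 | 91.4% |
| 0.5 | 0.80 | 87.8% | 0.82 | 87.2% |
| 0.7 | 0.91 | 83.5% | 0.93 | 82.8% |
| 0.8 | 0.96 | 81.4% | 0.98 | 80.6% |
| 0.9 | 1.02 | 79.3% | 1.03 | 78.5% |

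Simulation with 20,000 trials per setting gave ratios of 0.69, 0.80, 0.92 and 1.02 at N = 50 for rho 0.3, 0.5, 0.7 and 0.9.

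**Step 4: chance imbalance.** The SE of the baseline difference is √(2/25) = 0.283 SD, so its 95% range is ±0.55 SD; at 20 per arm it is ±0.62 SD. With k = 1 the change estimate shifts by −(1 − rho) times the imbalance. At rho 0.5 and an imbalance of 0.55 SD, the shift is about 0.28 SD. The simulated slopes were −0.70, −0.50, −0.29 and −0.10 at rho 0.3, 0.5, 0.7 and 0.9. For the adjusted model they were about 0.

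**Step 5: unequal variances.** With k = 1.3 (assumed), the step 1 ratio at rho 0.5, 0.6 and 0.7 is 1.2675/1.39 = 0.91, 1.0816/1.13 = 0.96 and 0.8619/0.87 = 0.99. After the factor 1.068 these become 0.97, 1.02 and 1.06. With k = 0.8 and rho 0.5 the step 1 ratio is 0.48/0.84 = 0.57, a larger gain than at k = 1.

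**The case against.** The strongest reply is that nothing here is wrong. A two-sample t-test on change is unbiased over repeated randomisations and holds its type I error. These are secondary endpoints of a declared pilot with no power claim attached, and the effect estimate passed to the next trial is noisier but not biased. This stands, and it sets the level of the point.

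The size is also uncertain. The entry rule truncates baseline dizzy days but not follow-up, so follow-up SD may exceed baseline SD, and step 5 shows the gain can then shrink to nothing or turn into a slight loss. This stands too, though a smaller follow-up SD works the other way.

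Three stronger readings are tempting, and the documents do not support them.

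- **That regression to the mean biases the comparison.** The plan raises it as a weakness of cohort studies, and its Bias section relies on the placebo arm to deal with it. That works on average over randomisations. What remains is the effect of an imbalance in this one trial.
- **That omitting the strata must widen the standard error.** This is so only if sex or diagnosis predicts outcome, and no evidence on that is given. Omitting prognostic strata would make the test conservative, not invalid.
- **That the gain is at least 5 power points up to rho 0.7.** Charging the variance cost of one covariate gives about 93, 89, 85 and 83% at rho 0.3, 0.5, 0.7 and 0.8. The model with both strata has the lower figures in the table.

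**Conclusion.** The point holds as an inexpensive improvement to the secondary analyses. The planned tests, read as two-sample tests on change, are valid but generally less precise than a baseline-adjusted analysis, and they leave a conditional error of −(1 − rho) times any chance imbalance.

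Under equal variances and non-prognostic strata, the gain over an 80% reference at 25 per arm is about 12, 8, 4 and 1 points at rho 0.3, 0.5, 0.7 and 0.8. It has gone near rho 0.9. Most of it comes from the baseline value; the strata's share cannot be determined.

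Two wording defects belong with this point. Paired cannot describe a comparison of independent arms, and the summary and analysis sections disagree on it for dizzy days and DHI. The baseline time for DHI and PROMIS also differs between the text and what the schedule appears to show.

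**What to change.** In the Statistical Methods summary and in Analysis of Secondary Endpoints, replace the t-tests for dizzy days (months 3-4), DHI (month 4) and the PROMIS physical and mental T-scores (month 4). For each, prespecify before unblinding a linear model of the follow-up value on arm, the pre-treatment value of the same measure, sex, and definite or probable status. Report the adjusted arm difference with its 95% CI. Dizzy days are a bounded count, so use robust standard errors or add a count-model sensitivity analysis.

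Drop the word paired throughout. Define baseline as the last pre-dose value, and reconcile month 0 in the text with the schedule. Keep the 50% responder chi-squared test and the category percentages as they are.

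The cost is SAP wording only, with no new data, visits or staff. The statistical price is three covariate degrees of freedom, which costs slightly if rho is very high, or if follow-up SD is well above baseline SD, and the strata are not prognostic.

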- Diagnosis of definite or probable vestibular migraine per Barany society criteria
- Baseline (SV1) and SV2 VM-PATHI score > 25
- Baseline (month 0 to 1) definitive dizzy days > 4
- Fluency in English
- 80% adherence or better to daily SMS during baseline phase
- Written informed consent
- Access to email, and cell phone

Exclusion criteria

- Vestibular hypofunction (unilateral or bilateral)
- History of ear surgery (other than ear tubes)
- Other vestibular diagnosis (excluding treated BPPV- Benign Paroxysmal Positional Vertigo).
- Failure of treatment with > 4 prophylactic migraine medications
- Prior or current treatment with a CGRP medication
- Pregnant/breastfeeding if female
- History of serious medical or psychiatric disease, at the discretion of the treating physician (including significant coronary artery disease, peripheral vascular disease, cerebrovascular disease, kidney disease, liver disease, and uncontrolled psychiatric disease or past psychiatric hospitalization)
- Unwilling to use approved form of birth control during the study
- Ok if on up to 2 migraine prophylactic medications (prescribed for that purpose), dose must be stable for 2 months prior to study start.

Study design: Interventional

Randomization Radio: 1:1 placebo: 120 mg galcanezumab (with 240 mg loading dose at month 1)

Comparator Description: Subjects will be compared between active treatment and placebo groups

IND: exempt

Off Label: no

Sample size: 25 per arm, or 50 total

Sample size justification: This is intended to be a pilot study, as there is currently no data available. Therefore, one main aim of this study is to better inform sample size calculations for a larger study. We have chosen 50 subjects, or 25 per arm, as a reasonable number that should help provide data to inform whether or not a larger study would be useful, assuming a 10-20% drop out rate.

Scientific Justification and background:

The objective of this study is to address whether galcanezumab is more effective than placebo at reducing dizziness in patients with vestibular migraine. Vestibular migraine is a distinct subtype of migraine that causes episodic vertigo/dizziness, sometimes with headache, and sometimes without. However, unlike traditional migraines, patients generally seek out care

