These inclusion/exclusion criteria were chosen so that the study has as much real world applicability as possible, while also minimizing risks to subjects. Based on our preliminary data, we believe that with these inclusion and exclusion criteria, and accounting for subjects who don't want to participate and also dropout, we will still be able to recruit enough subjects to meet our recruitment goals within 2 years.

Sample Size:

We have specifically designed this as a pilot study due to lack of data to help inform sample size calculations. However, hypothesizing a difference between VM-PATHI scores between groups of 7 points, and using the standard deviation from the validation of the instrument, we with 50 subjects total, or 25 per arm, we will have 90% power to detect a significant difference at the 0.05 level between groups to assess the efficacy of galcanezumab for vestibular migraine. If we assume a 10% dropout rate in the trial we will still have greater than 80% power to detect a difference.

Clinical Sites:

We will perform this study as a single center. We will be recruiting subjects from both the Otolaryngology-Head and Neck Surgery and Neurology departments. In a previous study where we developed the VM-PATHI, we were able to recruit around 80 subjects with vestibular migraine in a little over 1 year.

Study Visit Timeline:

The study visits will be scheduled within +/- 4 days of the expected timeline. This flexibility is based on the clinic availability dates of the PI and other providers.

- Study Visit 1 (SV1) = Day 0 / Month 0
- Study Visit 2 (SV2) = Day 30 / Month 1
- Study Visit 3 (SV3) = Day 60 / Month 2
- Study Visit 4 (SV4) = Day 120 / Month 4

Re-Enrollment Policy:

For participants who met all inclusion criteria AND none of the exclusion criteria (except for not having the minimum required VM-PATHI score and/or definitive dizzy days), they can re-enroll in the study at a later date when they feel their symptoms are worse. At that time, the participant would have to start over from Day 0 and undergo screening again.

Randomization:

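### The primary t-test is labelled intent-to-treat but can use only subjects with a month-4 VM-PATHI, while 15-20% loss is expected and after-loss power is stated only at 10%

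*Combined protocol and SAP*

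**What the plan says.** The combined protocol and SAP gives a loss rate in three places.

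- **Sample size justification (synopsis):** 50 subjects should be enough "to inform whether or not a larger study would be useful, assuming a 10-20% drop out rate". No power is attached.
- **Sample Size:** for a 7-point difference with 50 subjects, "or 25 per arm, we will have 90% power to detect a significant difference at the 0.05 level between groups". The spread comes from "using the standard deviation from the validation of the instrument", and no number is printed. Then: "If we assume a 10% dropout rate in the trial we will still have greater than 80% power".
- **Missing Data:** "We anticipate a 15-20% loss to follow up, and have accounted for that in our sample size calculations".

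The primary analysis (Statistical Methods; Analysis of Primary Endpoint) is a two-tailed t-test, described as paired, of change in VM-PATHI to month 4 between arms. Of it the plan says: "This will be conducted with an intent-to-treat analysis". Missing Data adds: "Outliers and non-compliant subjects will be included in the analysis. We will perform an intent-to-treat analysis". Pharmacy/Study Drug also keeps in the analysis those who do not take drug. Under Early Discontinuation of Study Drug, subjects who stop treatment "should be encouraged to complete all remaining scheduled visits and procedures".

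The Data Analysis Plan requires completed questionnaires for the per-protocol group. It places other treated subjects in an intent-to-treat group. No section says how a subject with no month-4 VM-PATHI enters the primary comparison.

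**The concern.** Two questions arise. The first is whether the claim that 15-20% loss was accounted for can be traced to a calculation, since the only after-loss figure is at a lower rate. The second matters more: whether the analysis can deliver what its label promises. Change to month 4 cannot be computed without a month-4 score. Unless a rule supplies one, the t-test becomes an analysis of subjects who reached the final visit, and randomisation no longer protects the comparison.

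The synopsis says the pilot should inform whether a larger trial is useful, and the background gives effect size for planning as the purpose. A biased difference would carry straight into that planning. Without a written rule, the handling of up to one in five primary outcomes is also left to be settled late.

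**Working it through.** **Inputs.** From the plan: difference 7 points, 25 per arm, two-sided alpha 0.05, power 90%, loss rates 10%, 15% and 20%. The SD is not printed, so it is solved from the 90%. The 90% itself therefore cannot be checked.

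**Step 1: the plan's own figures.** For a two-sample t-test the noncentrality is d × √(n/2), where d = difference/SD. Power of 90% at n = 25 requires d = 0.936, so SD = 7/0.936 = 7.48, and the noncentrality is 0.936 × √12.5 = 3.31. With lost subjects missing, n = 25(1 − p):

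| Loss p | n per arm | Noncentrality | Power |
|---|---|---|---|
| 0 | 25 | 3.31 | 90% (input) |
| 10% | 22.5 | 3.14 | 86.6% |
| 15% | 21.25 | 3.05 | 84.5% |
| 20% | 20 | 2.96 | 82.2% |

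Normal-approximation check at 20%: (1.960 + 1.282) × √0.8 − 1.960 = 0.94, which gives 82.6%. Power reaches 80% only at about 24% loss (25% by the normal approximation). The statement of more than 80% at 10% is reproduced, and it also holds at 15% and 20%.

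**Step 2: an unfavourable sensitivity case.** Suppose every lost subject is kept in the analysis with no drug effect, and the 7 points apply only to subjects on treatment. The difference becomes 7(1 − p) = 6.3, 5.95 and 5.6. With n = 25 and SD 7.48, power is 83.1%, 78.7% and 73.7%. Adding the active-arm mixture variance 49p(1 − p) raises the pooled SD to 7.63, 7.69 and 7.74, and power becomes 81.6%, 76.5% and 70.8%. If half the lost subjects are missing and half are kept off drug, power is 84.8%, 81.6% and 77.8%.

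**Step 3: what the t-test does with missing scores.** Within an arm, with improvement counted as positive, the mean among retained subjects minus the mean among all subjects equals p × (retained mean − lost mean). If this gap exists in one arm only, it passes unchanged into the treatment difference. If it is equal in both arms, it cancels.

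An illustrative simulation used 20% loss, with loss in the galcanezumab arm related to the SV3 response, and a true difference of 7. The t-test on available month-4 scores gave about 7.8-7.9. A likelihood analysis using the baseline and SV3 scores gave about 6.9-7.0, with a smaller standard error.

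By the identity above, a bias of 0.8-0.9 at p = 0.20 corresponds to a gap of 0.8/0.20 = 4.0 to 0.9/0.20 = 4.5 points between retained and lost galcanezumab subjects. That is 0.53 to 0.60 of the back-solved SD. The loss mechanism is an assumption, not something the plan states. Loss of the opposite kind would bias the estimate downwards.

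**Step 4: what data are available.** Appendix 1 schedules VM-PATHI at all four visits. A subject lost between SV3 and SV4 therefore already has an on-treatment score, which the planned test ignores.

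**The case against.** The strongest reply is that nothing printed is wrong. Power stays above 80% at 20% loss when lost subjects are missing, so the claim to have accounted for 15-20% can be defended, and the synopsis range of 10-20% contains both other rates. This stands. The mismatch is a matter of clarity.

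A reader might go further and infer that the trial is underpowered, at about 71-79% for 15-20% loss under intent-to-treat. The documents do not support that. The Missing Data rate is for loss to follow-up, meaning subjects likely to have no final score. The retention provisions concern subjects who stop drug, or do not take it, and are still measured, and no rate is given for them. Nothing says lost subjects are assigned zero effect. The Sample Size section does not describe the 7 points as an on-treatment difference. If 7 is already the as-randomised difference, the dilution does not apply.

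It can also be said that this is a pilot, that a coordinator helps subjects complete the forms, and that allocation is kept secret until after analysis. These points limit the amount of missing data and any choice of method by arm. They do not say what happens to a missing score, and blinding does not remove bias from selective loss.

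**Conclusion.** The point holds as a missing-data and analysis-method problem. With the plan's own expected loss, about 8 to 10 of 50 randomised subjects (0.15 × 50 = 7.5; 0.20 × 50 = 10) would be absent from a test described as intent-to-treat, with no rule for them. The estimate is biased if loss relates to response differently in the two arms. The illustration puts this at close to 1 point on a true 7, under an assumed mechanism.

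The power part is minor. Conditional on the stated 90%, power is about 87%, 85% and 82% at 10%, 15% and 20% loss. Figures below 80% at 15-20% belong in a labelled sensitivity case at most. They are not evidence of a wrong sample size.

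**What to change.** 1. **Analysis of Primary Endpoint and Statistical Methods:** replace the paired t-test with a between-arm mixed model for repeated measures on VM-PATHI change at SV3 and SV4. Use the pre-treatment score as covariate and the month-4 contrast as the primary result. Include all randomised and treated subjects with any post-baseline score. Name which pre-treatment visit supplies the baseline, since the primary objective uses month 0 and the analysis section month 1.
2. **Missing Data:** add one sensitivity analysis that gives lost galcanezumab subjects placebo-like outcomes. This can also cover those lost before SV3, whom the change model cannot include.
3. **Sample size justification, Sample Size and Missing Data:** use one loss rate. Extend the power sentence to about 82% at 20% loss, and print the SD, saying whether it is for a score or a change.

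Keep N at 50. No subjects, visits or assessments are added. The cost is slightly more analysis work and reliance on a missing-at-random assumption, which the sensitivity analysis tests.
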